Appendix 8: Guidelines for the management of hypotension 10.8

- 1. Investigator should monitor blood pressure closely.
- 2. If symptomatic hypotension occurs:
 - Correct any treatable cause, e.g. hypovolemia
 - If hypotension persists, any antihypertensive drug and non-disease-modifying drugs, such as diuretics, calcium channel blockers (CCBs), nitrates, and α-blockers, should be down-titrated or stopped first before down-titration of the study drug is considered
 - If hypotension persists, the study drug should be down-titrated or even temporarily withdrawn.

10.9 Appendix 9: Treatment guidelines for elevated potassium and hyperkalemia (serum potassium ≥ 5.3 mmol/L)

General principles

Elevation of potassium levels on a non-hemolyzed specimen above the predefined values should be repeated and confirmed before any action, if appropriate based on investigator's medical judgment.

For assessment of potassium, no blood sample should be drawn by finger or heel stick. Also note that pH can affect potassium values, and that abnormal potassium values should include assessment of pH. Each 0.1 increase in pH represents a 0.6 mEq/L change in the opposite direction of the pH change.

Patients with elevated potassium value will be managed according to the corrective actions outlined below. Hyperkalemia should be followed until resolution.

Corrective action for management of elevated potassium and hyperkalemia

Serum potassium > 5.2 and ≤5.4 mmol/L

Confirm potassium concentration in a non-hemolyzed sample.

Reinforce low potassium diet and restriction of food/drinks with high potassium content (e.g. orange juice, melon, bananas, low-salt substitutes etc.).

Review medical regimen (including dietary supplements and over-the-counter medications) for agents known to cause hyperkalemia. Consider reduction in dose or discontinuation of these agents:

- Aldosterone antagonists (if they are believed to be the most likely cause of hyperkalemia)
- Potassium-sparing diuretics (e.g. amiloride and triamterene) including in combination products with thiazide or loop diuretics
- Potassium supplements, e.g. potassium chloride
- Salt substitutes
- Non-steroidal anti-inflammatory drugs (NSAIDs)
- Cyclo-oxygenase-2 (COX-2) inhibitors
- Trimethoprim and trimethoprim-containing combination products, such as Bactrim® and Septra® (trimethoprim/sulfamethoxazole fixed combination)
- Herbal Supplements: For example, Noni juice, alfalfa (*Medicago sativa*), dandelion (*Taraxacum officinale*), horsetail (*Equisetum arvense*), nettle (*Urtica dioica*), milkweed, lily of the valley, Siberian ginseng, hawthorn berries.

Repeat serum potassium measurement within 3 to 5 days. If serum potassium remains > 5.2 and \le 5.4 mmol/L, regularly monitor serum potassium levels to ensure stability suggested once monthly.

Consider down-titration of study medication, according to investigator's medical judgment.

Serum potassium > 5.4 and < 6.0 mmol/L

Confirm potassium concentration in a non-hemolyzed sample.

Consider down-titration or temporarily discontinue study drug according to investigator medical judgment.

Apply all measures outlined for serum potassium > 5.2 and ≤ 5.4 mmol/L.

Repeat serum potassium measurement after 2-3 days.

• If serum potassium < 5.4 mmol/L, consider resumption of study drug at lower dose with repeat potassium within 5 days.

Serum potassium ≥ 6.0 mmol/L

Confirm potassium concentration in a non-hemolyzed sample.

Urgently evaluate patient and treat hyperkalemia as clinically indicated.

Apply all measures outlined for serum potassium > 5.4 and < 6.0 mmol/L.

Study drug should be immediately interrupted or discontinued if the serum potassium is greater than or equal to 6.0 mmol/L.

No resumption of study drug without individualized case discussion with and permission from Novartis medical monitor or his/her designee.

10.10 Appendix 10: Reference table – blood volume by weight

Table 10-6 Reference table – blood collection volumes by body weight (kg)

2.5% and 5% Blood volume table by weight (up to 35 kg)¹

Body Total blood Weight volume of the		Maximum allowable volume (mL) in one blood draw	Total maximum volume (mL) drawn in a 28-day period
(Kg)	patient (mL)	(= 2.5% of total blood volume of the patient)	(= 5% of total blood volume of the patient)
2.5	200	5	10
3	240	6	12
3.5	280	7	14
4	320	8	16
4.5	360	9	18
5	400	10	20
5.5	440	11	22
6	480	12	24
6.5	520	13	26
7	560	14	28
7.5	600	15	30
8	640	16	32
8.5	680	17	34
9	720	18	36
9.5	760	19	38
10	800	20	40
10.5	840	21	42
11	880	22	44
11.5	920	23	46
12	960	24	48
12.5	1000	25	50
13	1040	26	52
13.5	1080	27	54
14	1120	28	56
14.5	1160	29	58
15	1200	30	60
15.5	1240	31	62
16	1280	32	64
16.5	1320	33	66
17	1360	34	68
17.5	1400	35	70
18	1440	36	72
18.5	1480	37	74
19	1520	38	76
19.5	1560	39	78

Body Weight (Kg)	Total blood volume of the patient (mL)	Maximum allowable volume (mL) in one blood draw (= 2.5% of total blood volume of the patient)	Total maximum volume (mL) drawn in a 28-day period (= 5% of total blood volume of the patient)
20.5	1640	41	82
21	1680	42	84
21.5	1720	43	86
22	1760	44	88
22.5	1800	45	90
23	1840	46	92
23.5	1880	47	94
24	1920	48	96
24.5	1960	49	98
25	2000	50	100
25.5	2040	51	102
26	2080	52	104
26.5	2120	53	106
27	2160	54	108
27.5	2200	55	110
28	2240	56	112
28.5	2280	57	114
29	2320	58	116
29.5	2360	59	118
30	2400	60	120
30.5	2440	61	122
31	2480	62	124
31.5	2520	63	126
32	2560	64	128
32.5	2600	65	130
33	2640	66	132
33.5	2680	67	134
34	2720	68	136
34.5	2760	69	138
35	2800	70	140

Blood volume drawn for the purpose of this study is limited to a maximum of 2.5% of the circulating blood volume per sampling session and to a maximum of 5% over a 4-week period (Howie 2011). Investigators may further limit the volume of blood withdrawn based on local institutional guidelines and if the clinical condition of the patient may be adversely affected by removal of the blood volumes stated above.

¹ For body weights >35 kg, use the following formulas to calculate 2.5% and 5% of total blood volume:

^{2.5%} of total blood volume = body weight (in kg to the closest 0.5 kg) X 2

^{5%} of total blood volume = body weight (in kg to the closest 0.5 kg) X 4

11 References

References are available upon request

Clinical Development

LCZ696/ Sacubitril Valsartan Sodium Hydrate /Entresto®

CLCZ696B2319E2 / NCT06149104

A multicenter, open-label study to collect the safety information of sacubitril/valsartan in Japanese pediatric patients with heart failure due to systemic left ventricle systolic dysfunction who have completed CLCZ696B2319E1 study

Statistical Analysis Plan (SAP)

Author: Trial Statistician

Document type: SAP Documentation

Document status: Final

Release date: 30-August-2024

Number of pages: 24

Property of Novartis

Confidential

May not be used, divulged, published or otherwise disclosed without the consent of Novartis

Template Version 6.0, Effective from 23-Nov-2022

Document History – Changes compared to previous final version of SAP

Date	Time point	Reason for update	Outcome for update	Section and title impacted (Current)	
27- Nov- 2023	Prior to DB lock	Creation of final version	N/A - First version	NA	
30- August 2024	Prior to DB lock	To Add software used for analysis	Unless otherwise specified, the data will be analyzed according to the study protocol using SAS® 9.4 or higher and current version R® at time of analysis, by Novartis personnel.	2.1 Data analysis general information	
30- August	Prior to DB lock	To clear the definition of	Each scheduled visit is defined using the study day as follows:	2.1.1 General definitions	
- 2024		each scheduled visit	· Visit $3M = day 91$		
		, 1511	· Visit $6M = day 183$		
30- August - 2024	Prior to DB lock	To correct a typo	The z-score formula is corrected.	2.3.2 Demographics and other baseline characteristics	
30- August - 2024	Prior to DB lock	To clear the definition of the visit date	The dose level for each visit is defined as the dose level of dosing interval with its start date prior to or equal to the scheduled visit date and its end date later than or equal to the scheduled visit date. For EOS visit, actual visit date is used to identify the dose level.	2.4.1 Study treatment/compliance	
30- August - 2024	Prior to DB lock	To correct the summarization category	summarized by medication category and preferred term	2.4.2 Prior, concomitant and post therapies	
30- August - 2024	Prior to DB lock	To remove RMP text from description of	The following treatment emergent adverse event of special interest will be summarized.	2.7.1.1 Advers e events of special interest	

ovartis	Confidentia
AP v2	

Date	Time point	Reason for update	Outcome for update	Section and title impacted (Current)

ARB	Angiotensin Receptor Blocker
CRF	Case Report Form
CSR	Clinical Study Report
eCRS	electronic Case Retrieval Strategy
EOS	End of Study
ENR	Enrolled Set
MedDRA	Medical Dictionary for Drug Regulatory Affairs
MRAs	Mineralcorticoid Receptor Antagonists
PDs	Protocol deviations
PK	Pharmacokinetics
SAF	Safety Set
SAP	Statistical Analysis Plan
SGLT2i	Sodium-GLucose co-Transporter2 inhibitor
WHO	World Health Organization

Introduction 1

This Statistical Analysis Plan (SAP) describes details of the analyses as outlined in section 9 of the study protocol. Results will be summarized in the clinical study report (CSR).

1.1 Study design

This study (CLCZ696B2319E2) is a multicenter, open-label extension study for Japanese patients who have successfully completed the CLCZ696B2319E1 (PANORAMA-HF OLE) study (Figure 1-1). PANORAMA-HF OLE study is an on-going Phase 3b study in pediatric patients with systemic left ventricular systolic dysfunction to evaluate long- term safety and tolerability of sacubitril/valsartan in eligible CLCZ696B2319 (PANORAMA-HF) participants.

Only Japanese patients who successfully completed PANORAMA-HF OLE study and fulfill protocol requirements are eligible to participate in this study, and will be offered the option to initiate treatment with sacubitril/valsartan by enrolling into this study at the discretion of the Investigator. Participants who permanently discontinued study drug treatment during PANORAMA-HF OLE study are not eligible for this study.

For all consenting patient's eligibility for this study will be assessed at the first visit (Visit Day1) and the study medication will be initiated. The first visit (Visit Day1) is the same day as the End of Study visit (Visit 599) of PANORAMA-HF OLE study.

The starting dose of study drug will be determined by the Investigator considering the participant's condition. The dose level of open-label sacubitril/valsartan at the end of study visit of PANORAMA-HF OLE study may remain the same, or the dose level may be changed at the discretion of the Investigator.

Study Duration:

Actual duration depends on the timing of sacubitril/valsartan formulation for pediatrics available on the market in Japan.

Treatment Duration:

Until marketed product of pediatric formulation is available in Japan

Visit Frequency:

Every 3 months (including telephone visits)

Treatment of interest

The investigational treatment sacubitril/valsartan

Number of Participants:

A maximum of 8 Japanese patients will be enrolled into the study.

[figure not shown]
Key Inclusion criteria

- 1. Signed informed consent as well as assent at an appropriate age must be obtained prior to participation in the study.
- 2. Male or female, inpatient or outpatient, and < 18 years of age (at the time of signing informed consent).
- 3. Patients who have completed PANORAMA-HF OLE study and are able to be safely enrolled into this study as judged by the Investigator.

Key Exclusion criteria

- 1. Patients who permanently discontinued the study drug treatment during PANORAMA-HF OLE study.
- 2. Renal vascular hypertension (including renal artery stenosis).
- 3. Patients with a history of angioedema.
- 4. Patients who have parents or legal guardians who do not give consent or allow the child to give assent, or inability of the patient or the parents/legal guardians to follow instructions or comply with follow-up procedures.
- 5. Any medical condition(s) that may put the patient at risk in the Investigator's opinion, or that the Investigator deems unsuitable for the study.

Figure 1-1 Study design

EOS = End of study visit

- Visit Day1 is the same day as the End of Study visit (Visit 599) of CLCZ696B2319E1 study.
- This study will end when marketed product of pediatric formulation is available in Japan.

1.2 Study objectives, endpoints and estimands

The primary objective is to collect additional safety information of sacubitril/valsartan in the eligible Japanese patients who completed CLCZ696B2319E1 study.

There are no secondary or exploratory objectives for this study.

Table 1-1 Objectives and related endpoints

Objective(s)	Endpoint(s)	
Primary Objective(s)	Endpoint(s) for primary objective(s)	
	 Adverse events (AEs) 	

Objective(s)	Endpoint(s)
 To collect additional safety information of sacubitril/valsartan in Japanese patients after long-term treatment of sacubitril/valsartan in CLCZ696B2319E1 study 	

1.2.1 Primary estimand(s)

Not applicable

1.2.2 Secondary estimand(s)

Not applicable

2 Statistical methods

2.1 Data analysis general information

Unless otherwise specified, the data will be analyzed according to the study protocol using SAS® 9.4 or higher and current version R® at time of analysis, by Novartis personnel.

In general, continuous variables will be summarized using number of observations, mean, standard deviation, median, minimum and maximum. Categorical variables will be summarized using frequencies and percentages.

Study completion is defined as having reached the end of study visit (Figure 1-1).

Data from all study centers will be combined.

2.1.1 General definitions

- The study treatment is sacubitril/valsartan.
- The date of first administration of study treatment during this study is the day of the first non-zero dose of sacubitril/valsartan after patient is enrolled in CLCZ696B2319E2 study.
- The date of last administration of study treatment is the day of the last non-zero dose of sacubitril/valsartan.
- The study period starts with the date of the signature on informed consent (Visit Day 1, the same day as Visit 599 (EOS visit) of PANORAMA-HF OLE study) and ends with the date of end-of-study or premature study discontinuation visit (Visit EOS).
- The treatment period starts with the date of first administration of study treatment in CLCZ696B2319E2 study and ends with the date of treatment disposition. In the case that no EOS visit is undertaken (e.g., because the participant died or withdrew from the study without such a visit), the treatment period ends with the death/withdrawal date, or the last dose taken.
- Baseline is defined as the variable on the date of Visit Day 1 regardless of whether the study treatment is administered on Visit Day 1.
- Study day is defined as actual date date of Visit Day1 + 1

- Treatment day is defined as actual date the date of first administration of study treatment + 1
- Each scheduled visit date is defined using the study day as follows:
 - Visit M3 = day 91
 - Visit M6 = day 183

2.2 Analysis sets

The following analysis sets will be used for the statistical analyses:

- Enrolled set (ENR): All patients who signed the informed consent for the extension openlabel study.
- Safety Set (SAF): All ENR patients who received at least one dose of open-label study treatment during this extension open-label study.

The number of patients and percentage for all patients who enrolled in this study will be provided for each analysis set.

2.2.1 Subgroup of interest

No subgroup analysis will be provided in this study considering the small number of patients.

2.3 Patient disposition, demographics and other baseline characteristics

2.3.1 Patient disposition

The number and percentage of patients who don't meet a screen failure will be provided. For screen failures, the inclusion/exclusion criteria they did not meet will be summarized using the numbers and percentages of patients.

These summaries will be performed for the ENR.

The number and percentage of patients who complete the study, who discontinue from the study and the primary reasons for discontinuation will be summarized. In addition, the number and percentage of patients with protocol deviations (PDs) will be provided.

These summaries will be performed based on the SAF.

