5.5 Rule of exclusion criteria of analysis sets

PDs excluded from the ENR or SAF are shown in Table 5-1. Patients with only PDs that are not included in the list will not be excluded from any analysis sets.

Table 5-1 Protocol deviation criteria leading to exclusion from the analysis sets

PD ID	Description	ENR	SAF
INCL01A	No informed consent.	X	Х
INCL01C	ICF was not signed by subject/ parent/legal guardian; however, other family member signed on behalf the subject.	X	X

PD ID	Description	ENR	SAF
INCL02	Patients aged >= 18 was enrolled in the study.		Х
EXCL04A	Patient who has parents or legal guardians who do not give consent or allow the child to give assent.	X	Х

6 Reference

- 1. WHO Global Database on Child Growth and Malnutrition (Internet) Available from: [https://iris.who.int/bitstream/handle/10665/63750/WHO_NUT_97.4.pdf] (Accessed 11 September 2023).
- 2. COMPUTATION OF CENTILES AND Z-SCORES FOR HEIGHT-FOR-AGE, WEIGHT-FOR-AGE AND BMI-FOR-AGE (Internet) Available from: [https://cdn.who.int/media/docs/default-source/child-growth/growth-reference-5-19-years/computation.pdf] (Accessed 16 Oct 2023).

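### The protocol-deviation count is run on the Safety Set, so the four deviations that remove a participant from that set can never be counted in it

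*SAP*

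**What the plan says.** SAP 2.3.1 plans the deviation summary in one sentence: "In addition, the number and percentage of patients with protocol deviations (PDs) will be provided". It then fixes the population for that group of outputs: "These summaries will be performed based on the SAF".

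SAP 5.5 sets the exclusion rule: "PDs excluded from the ENR or SAF are shown in Table 5-1". The table has four rows. INCL01A ("No informed consent"), INCL01C ("ICF was not signed by subject/ parent/legal guardian; however, other family member signed on behalf the subject") and EXCL04A (parents or guardians withhold consent or do not allow assent) are marked for both the ENR and the SAF. INCL02 ("Patients aged >= 18 was enrolled in the study") is marked for the SAF only. All other deviations leave set membership alone: "Patients with only PDs that are not included in the list will not be excluded from any analysis sets".

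The set definitions in SAP 2.2 and Protocol 9.1 make the ENR those who signed consent and the SAF those in the ENR who took at least one dose. Neither mentions exclusion for a protocol deviation. On set sizes, SAP 2.2 adds: "The number of patients and percentage for all patients who enrolled in this study will be provided for each analysis set".

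**The concern.** The population of the deviation table is defined partly by not having the most serious deviations that the table should report. Deviations outside Table 5-1 remain countable, while the listed consent and eligibility deviations drop out. In a paediatric study these are the ones a reader would most want to see.

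At stake is the transparency of the study report. A participant who was dosed and then removed under Table 5-1 also leaves the adverse-event, exposure, laboratory and vital-sign outputs, all of which use the SAF. The deviation summary is the natural place to disclose that removal, and as specified it cannot do so. This holds whether or not the exclusions themselves are sensible.

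**Working it through.** The plan gives no figure to reproduce, so the check is one of set logic.

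**Step 1: Table 5-1 flags applied to the planned count.**

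| Deviation | Removed from ENR | Removed from SAF | Can enter a SAF-based count | Could enter an ENR-based count |
|---|---|---|---|---|
| INCL01A (consent) | yes | yes | no | no |
| INCL01C (consent) | yes | yes | no | no |
| EXCL04A (consent/assent) | yes | yes | no | no |
| INCL02 (age) | no | yes | no | yes |

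Four of four are uncountable on the SAF, and three of four would remain uncountable on the ENR. Moving the table to the ENR would therefore recover INCL02 only.

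**Step 2: illustration.** Take the maximum of 8 participants (SAP section 3) and assume that all 8 are entered and dosed. The number k with one listed deviation is an assumption; the plan gives no expected rate.

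| Deviation | k | SAF: cases / denominator | ENR: cases / denominator | All entered or dosed |
|---|---|---|---|---|
| Any consent deviation | 1 | 0 / 7 | 0 / 7 | 1 / 8 = 12.5% |
| Any consent deviation | 2 | 0 / 6 | 0 / 6 | 2 / 8 = 25.0% |
| INCL02 | 1 | 0 / 7 | 1 / 8 | 1 / 8 = 12.5% |
| INCL02 | 2 | 0 / 6 | 2 / 8 | 2 / 8 = 25.0% |

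The denominator moves as well. Suppose one participant has a listed deviation and a different one has an unlisted deviation. The SAF table gives 1/7 = 14.3%; on everyone entered or dosed it is 2/8 = 25.0%.

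**Step 3: could another planned output show the case?**

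- Set sizes (SAP 2.2): an INCL02 participant is in the ENR but not the SAF, so a gap may show. It carries no reason and is mixed with participants who consented but were never dosed. Consent deviators are in neither set.
- Unmet-criteria summary (SAP 2.3.1): run on the ENR and only for screen failures. It cannot reach the consent deviators. It reaches INCL02 only if that participant is classed as a screen failure.
- Demographics, exposure, concomitant therapy, adverse events, deaths, laboratory data, vital signs and growth (SAP 2.3.2 to 2.7.4.3): all on the SAF, including the listings.
- Deviation listing: none is described.

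**Step 4: where the exclusion comes from.** Exclusion for a deviation is stated only in SAP 5.5. Under SAP 2.2 or Protocol 9.1 alone, a consented and dosed participant aged 18 or over is in the SAF and would be counted. A participant who signed no form is outside the ENR, and hence the SAF, by definition even without Table 5-1. SAP section 4 records no change from the protocol's analyses.

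**Step 5: is a case plausible?** Protocol 5.1 requires age under 18 at consent. Protocol 4.1 calls those who reached 18 during the preceding extension study eligible if they qualify. A site relying on 4.1 could generate an INCL02 deviation. These two passages must be reconciled.

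**The case against.** A reader might infer that the report will print a row of 0 (0%) consent violations whatever happened. The documents do not support that. SAP 2.3.1 plans only an overall number and percentage, with no breakdown by category, and consent-process deviations outside Table 5-1 are still counted. What stands is narrower: the four listed deviations cannot contribute to the total.

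A reader might also infer that every excluded participant vanishes without trace. For INCL02 that is too strong. The participant stays in the ENR, and the protocol's definitions of a screen failure (5.3 and 10.2.2) do not expressly rule out someone already dosed, so the unmet criterion could be named there. The SAP does not say how such a participant is classed. For the consent deviations the point holds. Even if the percentages in SAP 2.2 were taken over everyone who entered, they would show at most an unexplained shortfall.

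The best structural objection is that the problem derives from the conflict between SAP 2.2 and SAP 5.5, so resolving that conflict might be enough. It might be for INCL02. It would not be for a participant who signed nothing, and while 5.5 stands as written the defect remains.

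Protocol 10.1.3 requires consent to data use, so a listing of participants without valid consent may be restricted. That limits what the listing may contain but does not justify a count that cannot register the event.

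Finally, the study is descriptive, tests no hypothesis, and may have no such deviation. That is fair: the effect is conditional on a case occurring.

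**Conclusion.** The point holds in this form. Under SAP 2.3.1 and 5.5 as written, 4 of 4 Table 5-1 deviations are excluded from the deviation count by construction and reduce its denominator. For 3 of the 4, a dosed participant is reported in no planned table or listing. For INCL02 the removal may be visible as an ENR–SAF gap, but without its reason unless the participant is classed as a screen failure.

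One case is at least 12.5% of the study, because enrolment cannot exceed 8. That is the weight of a case if it occurs, not an expected loss. The conclusion assumes that SAP 5.5 governs set membership over the plain definitions in SAP 2.2 and Protocol 9.1. It does not depend on whether the Table 5-1 exclusions are appropriate. This is a reporting defect that should be corrected; no hypothesis test or sample size is affected.

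**What to change.** In SAP 2.3.1, base the deviation summary on all participants entered in the study database or dosed in this study, before any Table 5-1 exclusion. Do not define that population by assigned participant number: Protocol 5.3.1 assigns the number on signing consent, so an INCL01A case with no signed form would still be missed.

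Add a short listing of Table 5-1 deviations giving the PD ID, dosed yes/no, and the set or sets from which the participant was excluded, limited to what the data-use consent rules allow.

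Reconcile SAP 5.5 with the SAF definitions in SAP 2.2 and Protocol 9.1, and record any resulting departure from the protocol in SAP section 4.

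The cost is one changed sentence, one listing of at most a few rows, the reconciliation wording, and a check of what may be shown for participants without valid consent. No new data collection is needed.
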